4.11.2 Clinical Laboratory Tests and Electrocardiogram

Clinical laboratory and ECG data will be presented for each treatment group using descriptive statistics based on the observed values and change from baseline values at each scheduled visit of the double-blind period, using the Double-Blind Safety Population. Summary statistics (n, mean, median, SD, minimum, and maximum) will be calculated for quantitative safety data and frequency counts will be compiled for classification of qualitative safety data. This will be repeated for visits corresponding to the open-label period, using the Open-Label Safety Population.

The number and percentage of patients with laboratory values that shift categories (i.e., below/within/above normal range) will be tabulated for each study visit and worst post-baseline visit during the double-blind period. This will be repeated using the Open-Label Safety Population as well as the Fosmetpantotenate Safety Population, for their respective treatment periods.

In addition, the number and percentage of patients with “potentially clinically significant laboratory values” (based on ranges defined below) will be summarized by treatment group, using the Double-Blind Safety Population and the Open-Label Safety Population.

Category	Parameter	Potentially Clinically significant ranges
Hematology	Hemoglobin	≤ 95 g/L (female), ≤ 115 g/L (male)
	Hematocrit	≤ 0.32 L/L(female); ≤ 0.37 L/L (male)
	Leukocytes	≤ 2.8 x 10 ⁹ /L
	Platelets	≤ 75 x 10 ⁹ /L; ≥ 700 x 10 ⁹ /L
Coagulation	PT-INR	≥ 2.0
	aPTT	≥ 43 seconds

Category	Parameter	Potentially Clinically significant ranges
Blood Chemistry	Calcium	< 1.75 mmol/L > 3.0 mmol/L
	Chloride	< 90 mmol/L > 115 mmol/L
	Creatinine	> 176.8 umol/L
	Glucose	< 2.8 mmol/L > 13.9 mmol/L
	Phosphate	< 0.6 mmol/L > 1.6 mmol/L
	Potassium	< 3.0 mmol/L > 5.5 mmol/L
	Sodium	< 130 mmol/L > 150 mmol/L
	Blood urea nitrogen	> 10.7 mmol/L
Liver Function Tests	Albumin	<25 g/L
	Total Protein	< 45 g/L
	ALT	> 3x-, 5x-, 10x-, and 20xULN
	AST	> 3x-, 5x-, 10x-, and 20xULN
	ALT and AST	Both ALT and AST > 3x-, 5x-, 10x-, and 20xULN
	Total Bilirubin	>ULN and >2xULN
	ALP	>2.5xULN
	ALT and Total Bilirubin	ALT >3xULN + total bilirubin > >2xULN, or international normalized ratio (INR) > 1.5
	AST and Total Bilirubin	AST >3xULN + total bilirubin > >2xULN, or international normalized ratio (INR) > 1.5

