4.11.3 Physical Examination and Vital Signs

Reported abnormalities during the double-blind period and open label period, will be tabulated by body system for patients in the Double-Blind and Open-Label Safety Populations, respectively. Changes in physical examinations will be described in the text of the final study report. A by-patient listing will be provided, which presents physical examination results across all assessments in the double-blind and open-label periods.

Vital signs (systolic and diastolic blood pressure, heart rate, respiration rate, and temperature), and body weight will be summarized by treatment group using descriptive statistics. Summary statistics (n, mean, median, SD, minimum, and maximum) will be calculated for both the actual value and the change from baseline value at each scheduled visit during the double-blind period. This will be repeated using the Open-Label safety population for visits during the open-label period.

For systolic and diastolic blood pressure, as well as weight, figures will be presented which show observed values, as well as change from baseline, by treatment group, for each visit during the double-blind period and open-label period, for patients in the Double-Blind and Open-Label Safety Populations, respectively.

In addition, the number and percentage of patients who meet the following criteria at any time during the double-blind period and open-label period will be summarized for each of the respective safety populations:

- Severe blood pressure elevation
 - Systolic blood pressure \geq 180 mm Hg; **OR**, diastolic blood pressure \geq 120 mm Hg
- Moderate blood pressure elevation
 - Systolic blood pressure \geq 140 mm Hg **OR**, diastolic blood pressure \geq 90 mm Hg

Patients with potentially clinically significant changes from baseline (i.e., elevated values per criteria above) will be summarized and flagged in data listings.

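### SAP 4.11.3 counts blood-pressure levels as changes from baseline, and its laboratory flags and physical-examination table omit the baseline comparisons set out in the protocol

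*SAP*

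**What the plan says.** **Blood pressure.** SAP 4.11.3 defines moderate elevation as systolic pressure of at least 140 or diastolic of at least 90 mm Hg, and severe elevation as at least 180 or at least 120. Neither class has a baseline or age term. Patients who meet a class "at any time during the double-blind period and open-label period will be summarized for each of the respective safety populations". The section then adds: "Patients with potentially clinically significant changes from baseline (i.e., elevated values per criteria above) will be summarized and flagged in data listings". Separately, vital-sign statistics are "calculated for both the actual value and the change from baseline value at each scheduled visit during the double-blind period", and this is repeated for the open-label visits.

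**Physical examination.** The same section says: "Reported abnormalities during the double-blind period and open label period, will be tabulated by body system". Changes are left to the narrative of the study report. Protocol 12.7.1 instead tabulates, by body system, the abnormalities found before the study and those found at its end.

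**Laboratory.** The text on the flag in SAP 4.11.2 reads: "potentially clinically significant laboratory values” (based on ranges defined below) will be summarized by treatment group". Limits for hematology, coagulation and chemistry, and for albumin and total protein, are absolute. Hemoglobin and hematocrit are split by sex. ALT, AST, total bilirubin and ALP are multiples of the upper limit of normal (ULN). No limit refers to the patient's own baseline or to age. The section also plans change-from-baseline statistics, and tables of shifts against the normal range at each visit and at the worst post-baseline visit. Protocol 12.7.2 asks in addition for a summary and a listing flag of patients with clinically significant changes from Baseline in laboratory values.

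**The concern.** A categorical safety table is read as a count of patients to whom something happened after dosing. The blood-pressure flag is named as such a count, but its definition measures something else: being above a level, whenever that began. A patient who entered the trial hypertensive and improved is reported alongside one who became hypertensive on drug.

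The laboratory and physical-examination tables are not misnamed in this way. Their problem is that the SAP is silent where the protocol sets out a comparison with baseline. Pre-existing laboratory abnormality can enter the trial, because Protocol 7.2 excludes it only if the investigator judges it clinically significant and a threat to safety. Every physical examination covers the neurological system (Protocol 9.3.1), and the disease is neurological. A raw count of abnormalities in that system may therefore say little about treatment.

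At stake is how readable these tables are in the interim report to regulators. In the open-label period, no concurrent placebo arm shows how much of a count was there before dosing.

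**Working it through.** The plan states no figure on this point. The check applies its rules to example values, compares the two documents, and illustrates the size under stated assumptions.

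**1. The blood-pressure rule applied to systolic values.** The cut-offs are from SAP 4.11.3; the example pairs are chosen here.

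| Baseline | Post-baseline | Change | Flag under the SAP |
|---|---|---|---|
| 150 | 142 | −8 | moderate |
| 182 | 181 | −1 | severe (and moderate) |
| 139 | 140 | +1 | moderate |
| 100 | 139 | +39 | none |
| 85 | 130 | +45 | none |

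Two falls are reported as changes from baseline, and two rises of about 40 mm Hg are not.

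**2. Whether a pre-dose reading can count.** The window is any time in the double-blind period. SAP section 3 lists the baseline visit, 1 to 2 days before dosing, among that period's study visits. The blood-pressure table states no restriction to post-baseline values. Read literally, an untreated reading alone can trigger the flag.

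**3. Protocol against SAP.**

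| Item | Protocol | SAP |
|---|---|---|
| Laboratory flag | significant changes from Baseline (12.7.2) | levels or multiples of ULN only (4.11.2) |
| Physical examination | pre-study and end-of-study findings tabulated (12.7.1) | findings during each period tabulated; changes in narrative only (4.11.3) |

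The SAP does refer to baseline elsewhere: treatment-emergent adverse events must be new or worsening (4.11.1), and the C-SSRS has shift tables (4.11.4). Protocol 10.3 uses a 2-fold rise over baseline for patients whose ALT or AST was already elevated.

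**4. Size.** Planned patients per arm: 82/2 = 41 (SAP 4.2). Let b be the share already above the cut-off who are above it again at some visit, and c the new-onset rate among the rest. Both are assumptions; neither is in the documents.

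Expected flagged proportion = b + (1 − b) × c.

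With no new onset (c = 0), flagged patients per arm = 41 × b: 2.1, 4.1, 8.2 and 12.3 for b = 5%, 10%, 20% and 30%. A count restricted to patients below the cut-off at baseline gives 0 in each case.

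Now assume new onset of 5% on placebo and 20% on active, a true risk ratio of 0.20/0.05 = 4.0 and a difference of 15 points:

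| b | Placebo | Active | Risk ratio | Difference, (1 − b) × 15 points |
|---|---|---|---|---|
| 5% | 0.0975 | 0.240 | 2.5 | 14.25 |
| 10% | 0.145 | 0.280 | 1.9 | 13.5 |
| 20% | 0.240 | 0.360 | 1.5 | 12.0 |
| 30% | 0.335 | 0.440 | 1.3 | 10.5 |

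The ratio is diluted heavily and the absolute difference modestly.

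**The case against.** The strongest reply is that baseline is not ignored. Blood pressure has change-from-baseline statistics and figures by arm. Laboratory data have change statistics and normal-range shift tables. All assessments are listed. Clinically significant laboratory abnormalities become adverse events (Protocol 9.3.3), and a DMC reviews safety. Randomization balances baseline status on average, and no test is planned on these flags.

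All of this stands, and it limits the point. A reader might infer that the safety analysis as a whole has no baseline reference; it plainly has. What remains is that mean changes do not identify patients, and normal-range shifts do not show who newly crossed one of the listed clinical limits.

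Four stronger readings are tempting but not supported:

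- **That laboratory abnormalities are also counted as changes.** SAP 4.11.2 calls them values, and the liver limits scale to ULN.
- **That the flags misfire in children.** Neither document gives pediatric norms or says whether the laboratory's reference limits are age-specific. The direction and size of any error, for creatinine or blood pressure, would rest on assumed figures. The documents show only that the absolute limits do not vary with age from 6 to 65 years, and that no age split is stated for these flags, whereas the adverse-event overview in SAP 4.11.1 has one.
- **That chance imbalance at baseline is itself the harm.** At 41 per arm, the noise around a flag rate is ordinary binomial variation and would be the same for a purely treatment-emergent rate of that size.
- **That nesting severe within moderate is an error.** It is cumulative reporting, as in the ULN rows, and exclusive counts follow by subtraction.

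**Conclusion.** The point holds for blood pressure on the SAP's own wording: a level is labelled a change, so the count is wrong for anyone elevated before dosing and misses large rises that stay below the cut-offs. It holds for laboratory flags and physical examination as a mismatch with Protocol 12.7.2 and 12.7.1. The primary and secondary tests are untouched.

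In the randomized period, pre-existing abnormality dilutes the contrast; on average it does not bias it towards either arm. In the open-label period, where SAP 4.12 makes long-term safety the main objective, no control arm offsets it. The sizes given (2 to 12 patients per arm; a risk ratio of 4.0 reduced to 2.5 to 1.3) rest on assumed baseline prevalences of 5% to 30%, persistence of the abnormality, and assumed onset rates. If few patients are abnormal before dosing, the effect is small. It merits correction because the rule is stated incorrectly and is cheap to put right.

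**What to change.** Before unblinding, amend SAP 4.11.2 and 4.11.3 as follows:

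- Count post-baseline values only, and say so.
- Cross-tabulate each blood-pressure and laboratory flag by baseline status. Give the treatment-emergent count among patients who did not meet the criterion at baseline, with those patients as denominator.
- Show worsening separately for patients who did meet it, for example by change from baseline. Simply excluding them would hide a rise from 145 to 175, which is moderate at both times and below severe.
- In open-label tables, also show status at the double-blind baseline for patients who had already received active drug. Otherwise an elevation that arose on drug would be counted as pre-existing.
- Restore the pre-study versus end-of-study physical-examination table.
- Present the flags by age group (pediatric, adult), and state whether the ULN values used are age-specific.

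The cost is a few more table rows and some programming on data already collected. No new assessments are needed.

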4.11.4 C-SSRS Scale

Columbia Suicide Severity Rating Scale is a suicide assessment questionnaire, which evaluates suicidal ideation and behavior. The questions after the screening visit are all based on “since last visit”.

Descriptive statistics will include the following tabulations by treatment group, with data pooled for pediatric and adult populations, across all visits of the double-blind period:

- The number (%) of patients with suicidal ideation or suicidal behavior at each visit: A “yes” answer at any time during treatment period to any one of the suicidal ideation and behavior questions.
- Shift tables that display the frequency of change in C-SSRS categories during the treatment period relative to baseline at each visit, as well as worst post-baseline visit.
- Severity, frequency, duration, controllability, deterrents, reason (for pediatric patients, only severity and frequency are collected) of suicidal ideation at each visit
- Actual and Potential Lethality/Medical Damage of Attempted Suicide (for actual attempts only) at each visit

The above tables will also be produced for visits in the open-label period, using the Open-Label Safety Population.

Data listings will provide individual patients’ responses to the C-SSRS questionnaire at all visits for each patient evaluated on this scale.

4.12 Open-Label Extension

Analyses of data collected during the open-label extension phase will be presented using methodologies similar to those described for the double-blind period. Since the main objective of the open-label extension phase is to evaluate long-term safety, efficacy measurements will mainly be summarized descriptively, with some hypothesis testing for exploratory purposes, as part of the Final Analysis. For the Interim Analysis, open-label safety data will be summarized and presented in listings, while open-label efficacy data will only be presented in listings.

4.12.1 Open-Label Efficacy Analysis

For the Interim Analysis, the scope of analysis of open-label efficacy data is limited to double-blind data. Open-label efficacy data will be included in the listings only.

A later version of the SAP will be released, which will describe the scope of open-label efficacy analysis for the Final Analysis. The analysis is outlined below:

The effects of fosmetpantotenate during the open-label use will be examined based on data from the OL-FAS.

For each efficacy endpoint collected in the open-label extension phase, scores will be tabulated using descriptive summary statistics (i.e., mean, SD, median minimum, and maximum for score totals; frequency tables for ordered categorical ratings) and graphical plots of mean values and mean change from baseline values at each study visit, overall

and by prior treatment in the double-blind period. For this purpose, baseline is defined as the last assessment prior to the first dose of open-label fosmetpantotenate.

On an exploratory basis, hypothesis testing will be applied to the primary and secondary efficacy endpoints measured during the open-label period to assess changes from Baseline, both overall and in the groups to which patients were initially randomized for the double-blind period (i.e., fosmetpantotenate or placebo). Between-group t tests will be used to explore whether improvement is greater for patients who convert to RE 024 from placebo, compared to those maintained on active investigational product for the open-label period. If the number of patients permits, mixed-effect linear models (as described for the primary efficacy analysis) may also be used to explore differences in the pattern of change over time between groups.

An additional exploratory analysis of PKAN-ADL may be undertaken using a mixed model, with Weeks since start of open-label treatment (continuous variable) as the fixed effect, baseline value (for the open-label extension period) as a covariate, and patient as the random effect. The first-order autoregressive AR(1) option will be used for modeling the covariance structure within-patient. The estimate of the time effect (i.e., rate of change) and its 95% CI will be obtained.

For all other efficacy measurements collected in the open-label extension phase, descriptive summary statistics will be presented by study visit. Graphs will be provided for each efficacy endpoint to display mean values (with standard errors) for all patients evaluated at each visit during the open-label extension period.

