Screening will take place within 29 days prior to the start of the double-blind period. Patients who fail screening for any reason may be re-screened up to 2 times. The protocol allows PKAN patients to be considered for participation three times (1 screening + 2 re-screening). If a given patient fails to qualify based on eligibility criteria, but the Investigator believes that this reason for non-qualification is a temporary situation, the patient can be screened a second time and a third time to determine whether he or she qualifies. Examples of such a situation include but are not limited to:

1. Abnormal labs suggestive of treatable, temporary abnormalities such as infection, anemia, dehydration, etc.
2. The patient had a major surgery within 30 days of screening, or DBS implantation within 6 months.
3. The patient has taken deferiprone within 30 days of screening.
4. The patient's symptoms are too mild to qualify with a PKAN-ADL Score < 6, but unfortunately it is possible that the disease will progress during the course of the trial enrollment such that the patient might qualify at a later date.

[figure not shown]
Assessment visits will occur at Baseline (Day -1), Days 1 through 4, and Weeks 3, 6, 12, 18, and 24. Patients may be admitted to an inpatient facility for safety monitoring from Baseline through completion of the Day 4 assessments for the double-blind period, or may be followed closely in a nearby outpatient setting. In order to provide training in proper administration, investigational product will be prepared and administered by site personnel, together with the patient and/or

family/caregiver, during in-clinic patient visits. Following adequate training, doses may be self-administered by the patient or caregiver at the site's discretion.

After the 24-week double-blind period, patients will receive fosmetpantotenate open-label for an additional 278 weeks. During the open-label period, assessment visits will occur at Weeks 27, 30, 36, 48, 60, 72, 84, 96, 108, and 120 and every 26 weeks thereafter (W146, W172, W198, W224, W250, W276, and W302). If the investigator determines that more frequent visits should occur after W120, additional unscheduled visits can be performed. Three-month (every 13 weeks) safety phone calls will be made in between each 6-month onsite visit following Week 120.

Flow charts depicting the study are presented in [Figure 1](#) and [Figure 2](#).

Figure 1: Study 024PKAN15004 Overview Flow Chart

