6.4. Discussion of Study Design, Including Choice of Control Group

The heterogeneity of signs, symptoms, and key phenotypic features (eg, age at onset, rate of progression, and survival duration) in patients with PKAN is a critical consideration in designing a clinical study for this disease. Placebo-control is necessary to control for variability in disease

severity and rate of progression. A randomized, placebo-controlled, parallel design study allows for a balanced distribution of uncontrolled variables across randomized groups, and a rigorous assessment of true drug effects on the outcome variables, controlling for nonspecific effects.

Demonstration of a clinically meaningful treatment effect over a 24-week period is sufficient to establish fosmetpantotenate as safe and efficacious for the treatment of PKAN, as there are no effective treatments available to date for this debilitating disease. The double-blind period of the trial will evaluate the efficacy of fosmetpantotenate in improving signs, symptoms, and functioning in patients with PKAN, and the safety extension will evaluate whether these improvements are generally maintained during an open-label treatment period that aims to simulate more real-world therapeutic conditions (eg, concomitant medications, which are fixed during the 24-week double-blind period, may be adjusted during the open-label extension based on medical judgment).

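### The outlined open-label slope model names no random slope, so its 95% CI for mean rate of change is too narrow if progression rates differ between patients (minor; optional exploratory analysis)

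*SAP*

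**What the plan says.** SAP 4.12.1 (Open-Label Efficacy Analysis) first defers the detail: "A later version of the SAP will be released, which will describe the scope of open-label efficacy analysis for the Final Analysis". It then outlines that analysis. The last model in the outline is introduced with "An additional exploratory analysis of PKAN-ADL may be undertaken using a mixed model", and its components are:

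- Fixed effect: "with Weeks since start of open-label treatment (continuous variable) as the fixed effect", with the open-label baseline value as covariate.
- Random effect: "and patient as the random effect".
- Errors: "The first-order autoregressive AR(1) option will be used for modeling the covariance structure within-patient".
- Result: "The estimate of the time effect (i.e., rate of change) and its 95% CI will be obtained".

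No random slope is named and no code is given for this model.

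Two other places bear on it. Protocol 6.4 treats as critical to the design "The heterogeneity of signs, symptoms, and key phenotypic features (eg, age at onset, rate of progression, and survival duration) in patients with PKAN". The Introduction (Protocol 4) likewise contrasts patients who die within a few years with others who decline slowly and live into their 30s to 50s. On timing, Protocol 6.2 states that in the open-label period "assessment visits will occur at Weeks 27, 30, 36, 48, 60, 72, 84, 96, 108, and 120 and every 26 weeks thereafter".

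**The concern.** The reported quantity is an average of patient slopes. If slopes differ, the variance of that average has two parts: measurement error around each patient's line, and the spread of the lines themselves. A model with a patient intercept and one common slope has no term for the second part. More visits per patient shrink the first part but not the second, so the understatement tends to be worse over long follow-up.

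AR(1) by visit order is a second, smaller mismatch. It gives one lag correlation to every consecutive pair of visits. PKAN-ADL is not taken at Week 27 (Protocol Table 15.1-2), so the gaps are 6, 12 and 26 weeks, or 13 after Week 120 if the phone assessments are used.

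At stake is the precision claimed for the on-drug rate of change. An interval that is too narrow could make a mean slope look better established than it is.

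**Working it through.** **Anchor from the plan.** SAP 4.2 assumes a difference of 3 points, SD 4.5 and 37 per arm, two-sided 0.05. The noncentral t distribution gives 80.8% power, so the stated figure of about 80% reproduces. Allowing for attrition, 74/0.9 = 82.2, consistent with 82 randomized. The documents give no precision figure for the open-label slope, so only SD 4.5 and N = 74 are carried forward.

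**Assumption.** Let a share q of the 24-week change variance (4.5² = 20.25) come from slopes that differ between patients. Then

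- slope SD per 24 weeks: σ_s = 4.5√q, which is 0.45, 1.01 and 1.42 for q = 0.01, 0.05 and 0.10;
- visit error variance: σ_e² = 20.25(1 − q)/2, so that σ_s² + 2σ_e² = 20.25.

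Larger slope SDs were set aside. A value of 2.25 implies an SD of 2.25 × 278/24 = 26 points over the extension, on a scale of 12 items scored 0 to 4 (0 to 48).

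**SE with a random slope.** With complete follow-up, SE = √[(σ_s² + σ_e²/Sxx)/74], where Sxx is the sum of squares of visit time about its mean, in 24-week units. The nine PKAN-ADL visits to Week 120 fall at 0.25, 0.5, 1, 1.5, 2, 2.5, 3, 3.5 and 4, so Sxx = 51.06 − 18.25²/9 = 14.06. The 16 on-site visits to Week 302 give Sxx = 570.03 − 76.58²/16 = 203.5. At q = 0.05 (σ_s² = 1.0125, σ_e² = 9.619):

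- Week 120: √[(1.0125 + 0.684)/74] = 0.151
- Week 302: √[(1.0125 + 0.047)/74] = 0.120

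**SE that the outlined model reports.** The large-sample fit of patient intercept plus AR(1) by visit order to such data gives 0.120 to Week 120 and 0.074 to Week 302. The second is below 1.006/√74 = 0.117, the floor that the spread of slopes alone sets.

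**Coverage.** Coverage = 2Φ(1.96 × r) − 1, where r is the reported SE over the true SE of the same estimator. Over slope SD 0.45 to 1.42, r runs from 0.92 down to 0.74 to Week 120, and lies between 0.61 and 0.73 to Week 302.

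| Slope SD per 24 weeks | To Week 120 | To Week 302, on-site | To Week 302, with phone |
|---|---|---|---|
| 0 | 95.0% | 95.0% | 95.0% |
| 0.45 | 93.0% | 76.5% | 69.9% |
| 1.01 | 87.7% | 77.0% | 69.6% |
| 1.42 | 85.3% | 84.5% | 79.9% |

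The Week 302 columns are not monotone because, as slope variance grows, the fitted AR(1) correlation rises and absorbs part of it. To Week 120, an intercept with no AR(1) would do worse at the top of the range: 92.2% falling to 74.5%.

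**Simulation check to Week 120** (REML, baseline covariate included):

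| Slope SD | Outlined model, complete (300 runs) | Random slope, complete | Outlined model, staggered (150 runs) |
|---|---|---|---|
| 0 | 95.7% | 96.3% | 96.0% |
| 0.45 | 92.7% | 94.3% | 92.0% |
| 1.01 | 87.7% | 95.3% | 94.0% |
| 1.42 | 85.0% | 97.7% | 87.3% |

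Monte Carlo error in the staggered column is about 2 points.

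**Spacing alone.** The truth here has no slope variance and a correlation that decays in real time (12-week correlation 0.2 to 0.95). AR(1) by visit order then covers 92.7% to 94.9%, a loss of 0.1 to 2.3 points.

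**The case against.** The strongest reply is that this is an optional outline. The model may or may not be run, is labelled exploratory, and belongs to the Final Analysis under a later SAP. At the interim, open-label efficacy data are only listed (SAP 4.10, 4.12). SAP 4.12 gives long-term safety as the extension's main objective, and SAP 4.10.4 treats open-label efficacy as exploratory. All of this stands and limits the severity. It does not remove the point: 4.12.1 presents this model as the outline of what the later version will contain.

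The absence of a random slope is also a reading of an incomplete specification. For the primary model, SAP 4.10.1 speaks of patient as a random effect, yet its code has only a REPEATED statement. So the SAP's random-effect wording does not settle the code. That is fair, but no reading of 4.12.1 as written supplies a patient-by-week term.

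Some stronger readings are tempting, and the documents do not support them:

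- **That the interval is too narrow regardless.** Heterogeneity is described only in words. At zero slope variance coverage is 95%.
- **That unequal spacing is a cause on a par with the missing slope.** On its own it costs little.
- **That the slope will be set against natural history to claim stabilisation.** Neither document plans that comparison.
- **That the Week 302 coverages are what the trial would see.** They assume complete linear follow-up, while patients may withdraw or move to commercial product (Protocol 6.3). With slope variance present, they rest on the large-sample calculation alone.

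**Conclusion.** The point holds conditionally and is minor. If progression rates differ between patients, as Protocol 4 and 6.4 say, the outlined model gives a 95% CI for the mean rate of change that is too narrow. The direction was the same at every non-zero slope variance in the large-sample calculation. The size depends on a slope variance that the documents do not give, and on linear slopes, 74 patients and complete follow-up. Within the assumed range the shortfall is about 2 to 10 points of coverage to Week 120 and about 10 to 18 points to Week 302 on on-site visits. Staggered follow-up to Week 120 gave 87% to 94%. The missing random slope drives the result. The primary, secondary and interim analyses are not affected.

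**What to change.** In SAP 4.12.1, and in the later SAP version, specify a random intercept and a random slope on weeks for each patient, with an unstructured 2×2 G matrix and Kenward-Roger degrees of freedom (already used for the primary model). If residual serial correlation is kept, replace AR(1) with a spatial-power structure in actual weeks.

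The change takes one sentence and two code options. It is best made before the interim, because the open-label efficacy listings will be visible after that and the covariance choice would no longer be blind to them.

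The cost is a wider interval: at slope SD 1.01 the SE per 24 weeks goes from 0.120 to 0.151 to Week 120, and from 0.074 to 0.120 to Week 302. The model may also fail to converge when many patients have short follow-up, so a fallback should be named. The random-slope interval still assumes linear change and ignorable dropout.
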